Appendix 7 Interview process for simulated buyers

The interview will be conducted online via Tencent Meeting. The interview time for each student (the simulated buyer) is about 10 minutes. The process is as follows:

1. Self-Introduction: Please give a brief self-introduction.
2. Recruitment Inquiry: How did you hear about our recruitment? Why do you want to participate in our research activities, and what do you hope to gain?
3. Research Overview: Introduce the key content of this research. Do you have any concerns or difficulties about participating fully? If there are difficulties that cannot be overcome, we suggest not participating.
4. Dress Code and Confidentiality: Additional information on dress code and confidentiality agreement (scientific rigor, data authenticity, innovation in research projects).
5. Safety Emphasis: Finally, we emphasize safety issues. We hope everyone will cooperate with us, return on time in the evening, and communicate with us if you have any arrangements or places you need to go.

Appendix 8 Survey sequence of the metropolitan areas for three teams

Team	Survey sequence
Team A	Harbin - Changchun - Shenyang - Dalian - Qingdao - Jinan - Shijiazhuang - Taiyuan - Beijing - Tianjin - Hohhot - Lhasa
Team B	Nanjing - Shanghai - Hangzhou - Ningbo - Fuzhou - Xiamen - Shenzhen - Guangzhou - Nanchang - Hefei - Urumqi - Xining - Yinchuan
Team C	Zhengzhou - Wuhan - Changsha - Nanning - Haikou - Guiyang - Kunming - Chongqing - Chengdu - Xi'an - Lanzhou

Appendix 9 Code for web crawling

```
#Rversion 4.04
setwd("E:/R")
library(xml2)
library(rvest)
library(dplyr)
library(stringr)
library(rjson)
library(jsonlite)
library(scales)
library(ResourceSelection)
library(openxlsx)#xlsx
library(sampling)
rm(list = ls())

# collect address and phone number using AutoNavi -----
key <- c("AutoNavi Key (got from AutoNavi API)")
storedf <- as.data.frame(matrix(nrow = 0, ncol = 8))
surveywords <- c("电子烟店", "电子烟零售店", "电子烟体验店", "电子烟集合店", "电子烟专卖店", "电子烟直营店", "雾化", "蒸汽烟", "vape", "电子烟旗舰店", "悦刻", "魔笛", "雪加", "小野", "铂德", "柚子 电子烟", "徕米", "MR 迷睿", "VTV", "福禄 FLOW", "RELX", "MOTI", "YOOZ", "snowplus", "vvild", "Boulder", "LAMI")

gGetstore <- function(keywords, city, page) {
  url <- paste0("https://restapi.amap.com/v3/place/text?keywords=", keywords, "&city=", city, "&citylimit=true&offset=20&page=", page, "&key=", key, "&extensions=all")
  data <- read_html(url, encoding='utf-8') %>% html_text()
  datalist <- fromJSON(data)
  address_islist <- 0 #check
  tel_more <- 0
  if (datalist$status == "1") {
    if (datalist$count != "0") {
      if (is.list(datalist$pois$address)) {
        datalist$pois$address <- sapply(datalist$pois$address, "[", 1)
        address_islist <- 1
      }
      df <- cbind(datalist$pois$id, datalist$pois$name, datalist$pois$address,
                  datalist$pois$location, datalist$pois$cityname, datalist$pois$adname,
                  datalist$pois$typecode)
      if (all(lengths(datalist$pois$tel) < 2)) {
        tel <- sapply(datalist$pois$tel, "[", 1)
```

```

}else{tel_more <- 1}

df<- cbind(df, tel)
}else{df <- 0}
}else{df <- 1}
storeout <- list(df=df, two=address_islist, three=tel_more)
return(storeout)
}

#run
cityname <- c("北京") #try each
store_city <- data.frame()
address_list <- rep(0,length(surveywords))
searchnm <- rep(0,length(surveywords))
storedf_class <- rep(0,length(surveywords))
tel_list <- rep(0,length(surveywords))
for (j in 1:length(surveywords)) {
  storedf <- data.frame()
  for (i in 1:100) {
    storelocation <- gGetstore(surveywords[j],cityname,i)
    storedf2 <- storelocation$df
    if(storelocation$two==1){address_list[j] <- 1}
    if(storelocation$three==1){tel_list[j] <- 1}
    if (is.numeric(storedf2)){
      searchnm[j] <- i
      break
    }else{
      storedf <- rbind(storedf,storedf2)
    }
  }
  storedf_class[j] <- class(storedf)
  store_city <- rbind(store_city,storedf)
  if(dim(storedf)[1] !=0){
    colnames(storedf) <- c("id","name","address","location","city","adname","typecode","tel")
    write.xlsx(storedf,paste0("E:/e_cig/summer_survey/retailer_list/list_",surveywords[j],"_",cityname,".xlsx"),
              append=T, overwrite=T)
  }
}
write.xlsx(store_city,paste0("E:/e_cig/summer_survey/retailer_list/city2/list_",cityname,".xlsx"),overwrite = T)
store_city <- unique(store_city)
write.xlsx(store_city,paste0("E:/e_cig/summer_survey/retailer_list/city/list_",cityname,".xlsx"),overwrite = T)

```

## **ABBREVIATION**

Abbreviation or Term	Definition/Explanation
E-cigarette	Electronic cigarette
RCT	Randomized controlled trial
ID	Identification card

# 1. Introduction

The Statistical Analysis Plan (SAP) aims to provide a comprehensive and detailed description of the methods and strategies to be adopted for analyzing data collected from e-cigarette stores in China. The SAP is finalized prior to database lock to ensure the credibility of the study's findings.

## 1.1. Overview

### 1.1.1. Study Design

This study is a two-armed, national-level, open-label cluster RCT conducted among e-cigarette stores located in 36 metropolitan areas across mainland China (including 4 municipalities directly under the Central Government, 27 provincial capitals, and 5 cities specially designated in the national plan). This RCT will adopt the mystery shopping approach to measure the effect of adolescent buyers' type of attire (school uniforms vs. casual attire) on the likelihood of sellers' compliance with the minimum age restriction for e-cigarette sales, defined by both age verification and sales. The e-cigarette stores will be randomly assigned to the intervention group or control group at a ratio of 1:1. Each store in the intervention group will receive a simulated buyer dressed in a school uniform, while each store in the control group will receive a simulated buyer dressed in casual attire. The simulated buyers in this study are adolescents aged 18-19 years old. The simulated buyers will attempt to purchase e-cigarette products and record the behaviors and marketing claims of the sellers, as well as store internal and external characteristics.

Eligible stores as study subjects will be identified from the AutoNavi Map through keyword searches. Stores are eligible for enrollment if they have reachable contact information and claim to be open for business on a regular basis when contacted. The expected number of e-cigarette stores sampled in each metropolitan area is approximately 32, with an additional 8 e-cigarette stores serving as backups, if the

number allows, for a minimum expected total enrollment of approximately 1,080 retailers. In addition, we plan to conduct the same trial for cigarette stores and perform a 1:1 match of e-cigarette stores and cigarette stores, allowing us to compare the business practices of e-cigarette stores and cigarette stores between the two attire groups.

### 1.1.2. Randomization

**Generating clusters to which the stores belong:** Considering traveling time and the efficiency of data collection, this trial will use a cluster randomization approach rather than simple randomization. Investigators will first map all the 40 selected stores within each metropolitan area and then divide them into clusters containing the same number of e-cigarette stores (approximately 5 stores per cluster), taking into account their locations and public transportation. Each cluster will then be digitally labeled, from area 1 to area 8. The labeling of the clusters will follow the principle of from top to bottom, and from left to right on the map.

**Assigning clusters to treatment and control groups:** Each cluster will be randomly assigned to one simulated buyer, and the type of attire (school uniforms or casual attire) they wear on a specific day will also be randomized. In this way, the e-cigarette stores will ultimately be allocated at a 1:1 ratio to either the intervention or control group.

- Specifically, the simulated buyers (data collectors) to be recruited are 18 to 19 years old, with a 1:1 ratio of males to females. To reduce bias associated with the personal characteristics of the simulated buyers, they will be randomly assigned a new digital number for each metropolitan area, which will be used for matching the clusters.
- The type of attire worn by each adolescent on a specific day will be pre-determined using Excel's random number generator within each sex, ensuring that each

adolescent has an equal probability of wearing school uniforms and casual attire during the entire study.

### **1.1.3. Blinding**

It will be impossible to blind study subjects (e-cigarette stores) regarding the assignment to the intervention or control group, as letting sellers in the e-cigarette stores see the buyers' attire is part of the treatment. However, sellers will not be aware of their participation in this trial due to the mystery shopping approach adopted.

The trial team, consisting of both simulated buyers and coordinators, will also not be blinded to the e-cigarette stores in the intervention and control groups, as there is no way to prevent them from knowing which e-cigarette stores have simulated buyers wearing school uniforms or casual attire on each day.

The statistician conducting the analyses will have no direct contact with the e-cigarette stores but will not be blinded to the treatment allocation.

## **1.2. Study Objectives**

### **1.2.1. Primary Objective**

To measure the effect of dressing in school uniforms (compared to casual attire) by adolescents on regulation compliance-related behaviors of e-cigarette sellers defined by both age verification and underage-cigarette sales.

### **1.2.2. Secondary Objectives**

- To determine the impact of type of attire by adolescents on in-store communication between sellers and customers, specifically dissuading use.
- To discern the differences in regulation compliance-related behaviors between e-cigarette and cigarette retailers.

### **1.2.3. Exploratory Objectives**

- To describe the regulatory compliance of e-cigarette and cigarette retailers across mainland China.
- To document the marketing and communication strategies adopted by e-cigarette and cigarette retailers, e.g. store location, advertisements, decorations and online delivery service, across mainland China.

### **1.3. Study Hypotheses**

We hypothesize that dressing in school uniforms by adolescents will significantly increase the likelihood of e-cigarette sellers verifying the age of buyers in stores and reduce the probability of their illegal sales to minors.

The corresponding null hypothesis that will be tested is that dressing by school uniforms by adolescents will have no effect upon e-cigarette selling behaviors in regulation compliance.

### **1.4. Sample Size**

Successful purchase rates of e-cigarette products for the school uniform group and casual attire group will be derived from the pilot study. Other parameters required for cluster-RCT sample size calculation are as follows:

- Randomization in a 1:1 ratio for the school uniform (intervention) group and casual attire (control) group
- $\alpha = 0.05$  (two-sided)
- power = 0.85
- cluster size = 4 (both for intervention group and control group)

- inter-cluster correlation coefficient = 0.5 (default)

However, considering the primary goal of this study is to characterize e-cigarette seller behaviors at a national level, we decide to set the final sample size to be approximately 1,080. This may be far more than the minimum sample required (about three times) for testing the effect of buyer attire on e-cigarette sales to adolescents in China.

## **2. Statistical and Analytical Procedure**

### **2.1. Study Subjects**

This study will be conducted across 36 major metropolitan areas in mainland China (including 4 municipalities directly under the Central Government, 27 provincial capitals, and 5 cities specially designated in the national plan). The expected number of study subjects sampled from each metropolitan area is approximately 32 e-cigarette stores, if the number allows, for a minimum expected total enrollment of approximately 1,080. This study will include cigarette stores for comparisons with e-cigarette stores. For each e-cigarette store, one nearby cigarette shop will be conveniently selected for matching, as cigarettes are widely available in convenience stores, supermarkets, and tobacco and liquor shops, making it impossible to systematically pre-identify these stores.

### **2.2. Study Variables**

#### **2.2.1. Outcomes**

##### **Primary Outcome Measure**

The primary outcome is the sales of e-cigarettes to adolescent buyers, measured by the successful purchase of e-cigarette products from the stores without showing any age proof.

##### **Secondary Outcome Measures**

- The seller verbally inquiring about the simulated buyer's age
- The seller requesting ID cards from the simulated buyer for age verification
- The seller dissuading the simulated buyers from using e-cigarettes

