5.3. Design and selection of the uniforms

In 2015, China's Ministry of Education, together with multiple departments including the National Standardization Committee, issued a directive titled 'Opinions on Further Strengthening the Management of School Uniforms for Primary and Secondary School

Students'.¹⁶ The policy, although not legally mandated, encourages students to wear school uniforms on weekdays. The decision on school uniforms is jointly made by the schools and committees of students' parents. However, once established in a school, it in reality becomes mandatory for all students to adhere to. Due to the fact that wearing school uniforms by secondary school students has become a social consensus, those wearing uniforms are naturally perceived as minors in China, especially when he/she looks young.

This study chooses school uniforms and casual attire as the indicator of being potential minors and adult buyers, respectively. The school uniform chosen is the most common style of middle/high schools in China, as the study will be conducted in thirty-six major metropolitan areas across mainland China. The casual attire style chosen is the most commonly seen in China. Appendix 3 shows pictures for adolescent models with pre-selected school uniforms and casual attire.

The same styles of school uniforms and casual attire with corresponding accessories, including school bags (adolescents), backpacks (male adults), and handbags (female adults), will be ordered and provided to simulated buyers free of charge.

6. Outcome Measures

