8.7. Missing data

Since simulated buyers use the instrument embedded in an online survey platform to fill out the collected information, there is no chance that they will miss any questions as the system will remind them of any potential missing values. The pilot survey will help us confirm which questions can be filled in, considering the possibility that the adolescents may be asked to leave by the sellers for not being able to show proof of age as soon as he/she enters the store. While filling in questions regarding the store external environment, simulated buyers can select "Unable to observe" and skip questions that cannot be answered. Missing data on the store internal environment due to the reason of being asked to leave will not affect our main analysis. For the in-store environmental characteristics, only subjects with available data will be included in the analyses.

9. Quality control

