- If a seller offers you to try an e-cigarette, they usually provide a disposable tool. Respond with, "This seems unsanitary, I won't use it... I'd rather buy a new one/I'd rather use my friend's."
- The seller might claim that the e-cigarette and cartridges are sold as a set, and that a friend's e-cigarette might not be compatible. You should insist on only buying the cartridges, "It's fine, I remember it's just like this one/... just buy a box of these."

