No, the e-cigarette store is not open (please skip to the end of the questionnaire and submit your answer sheet)

No, the seller is not in the store (please skip to the end of the questionnaire and submit your answer)

No, other _____ * (please skip to the end of the questionnaire and submit your answer sheet)

15. Is the tobacco retail license visible [Single choice question] *

Yes

No

16. Is there a "No use by minors" slogan in the store (excluding slogans on product packaging) [Single-choice question] *

Yes

No

17. Are there any of the following health warning signs in the store (excluding slogans on product packaging) [Single choice question] *

Yes, there is a "Smoking is harmful to health" sign

Yes, there is a "E-cigarettes are harmful to health" sign

Yes, both of the above exist

No

18. Are there children's toys, car models, figurines, and/or other decorations placed on the shelves or counters? [Note that these decorations need to be targeted at teenagers.] [Single Choice Question] *

Yes, specifically _____ *

No

19. Gender of the seller: (When there are multiple sellers, this question refers to the seller who communicates with the simulated buyer the most. The same applies to the questions below.)

Male

Female

20. Age of the seller (the simulated buyer needs to estimate) [Single-choice question] *

18-24 years old

25-29 years old

30-39 years old

>40 years old

21. Did the seller ask the simulated buyer if he or she was an adult? [Single Choice Question] * -----Questions such as "Are you an adult?" "Are you over 18?" "How old are you?" "Are you a student?" etc.

Yes

No

22. Did the seller ask to see the simulated buyer's ID? (If the seller requires you to fill in identity information on the system, please select Yes.) [Single Choice Question] *

Yes

No

23. Did the seller ask the simulated buyer to leave? (No sales communication) [Single Choice Question] * ----- If the seller does not check the age until the simulated buyer pays, the sales communication has been completed at this point. In this case, you should select "No" and continue to fill in the questionnaire.

○No

- Yes, the seller asked you (the simulated buyer) to leave without asking about their age. (Please skip to the end of the questionnaire and submit your answer.)
- Yes, the seller asked you (the simulated buyer) to leave after asking their age. (Please skip to the end of the questionnaire and submit your answer.)

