- Yes, the seller asked you (the simulated buyer) to leave after knowing that he or she did not have an ID card. (Please skip to the end of the questionnaire and submit your answer.)

In-store communication and records 2

24. Does the e-cigarette store sell the following types of e-cigarettes and accessories
[Multiple choice questions] **

Disposable e-cigarettes ----- Disposable e-cigarettes refer to those e-cigarettes that cannot be disassembled, refilled, or changed by the user and are thrown away after use. They can also be rechargeable. For example, the seller might describe them to you as "rechargeable for 1,000 puffs."

Reloadable e-cigarettes and/or cartridges ----- Reloadable e-cigarettes usually consist of two parts: a cigarette rod and a cigarette cartridge. The cigarette rod can be recharged and reused, while the cigarette cartridge is thrown away after use.

Open e-cigarettes that the user refills with e-liquid himself or herself ----- The e-liquid tank of open e-cigarettes is open and refillable. It can be refilled 3-6 times for continued use. The atomizer has a long service life.

Auxiliary accessories for e-cigarettes, such as protective cases, lanyards, etc.

Other, _____

25. Other items sold in the e-cigarette stores: [Multiple choice questions] *

No products other than e-cigarettes are sold

Power bank rentals

Addictive substances, such as tobacco, alcohol, and betel nut

Other _____

26. Did the seller proactively dissuade the simulated buyer from trying e-cigarettes? [Single Choice Question] * ----- The seller will tell you (the simulated buyer) that e-cigarettes are harmful, addictive, impossible to quit, don't try them, etc., in an attempt to discourage you from buying them.

Yes

No

27. The most popular flavor recommended to you (the simulated buyer) by the seller is [fill in the blank] * ----- Ask the seller, "With so many varieties, what are the differences?" and then, "Which one sells better?"

28. The second most popular flavor recommended to you (the simulated buyer) by the seller is [fill in the blank] * ----- If the seller only recommended one flavor in the previous question, you can fill in "none" for this question.

29. Is there a "Free Trial" sign or disposable filters in the store [Single-choice question] * -----Pay attention to whether there are disposable filters at the cashier]

Yes

No

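### Do the two age-check outcomes need changing because a seller who ejects the buyer unasked scores the same as one who sells unchecked?

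*SAP*

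**What the plan says.** SAP 1.1.1 treats compliance as having two parts, checking age and not selling. The hypothesis in SAP 1.3 has the same two limbs. The primary outcome (SAP 2.2.1) is a completed purchase with no proof of age. Two secondary outcomes carry the checking limb: verbal inquiry about age, and "The seller requesting ID cards from the simulated buyer for age verification".

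The data come from Protocol Appendix 4. Questions 21 (asked age) and 22 (asked for ID) are plain yes/no items. Question 21 is broad and counts "Are you a student" as asking. Question 23 covers visits that ended before any sales conversation. Its first positive option is "Yes, the seller asked you (the simulated buyer) to leave without asking about their age". The other two are ejection after an age question and being asked "to leave after knowing that he or she did not have an ID card". Any positive answer ends the form, so Question 26 (dissuasion) and Question 37 (purchase) stay blank.

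The SAP does not name Question 23 among its outcomes, covariates, descriptive summaries or subgroup analyses. The nearest planned result is in SAP 2.3.5: purchase rates split by age checking and attire. Protocol 8.7 foresees that buyers "may be asked to leave by the sellers for not being able to show proof of age as soon as he/she enters the store". It says that in-store data lost this way do not affect the main analysis, and it confines analysis of available data to the in-store environment items.

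**The concern.** Two opposite reactions get the same score. A seller who sees a uniform and turns the buyer out at once has acted on apparent age. A seller who hands over the product with no question has not. Both are No on Question 21 and normally on Question 22.

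The trial's own rationale makes an imbalance between arms plausible. Protocol 5.3 says that "those wearing uniforms are naturally perceived as minors in China, especially when he/she looks young". A seller who already takes the buyer for a minor has less need to ask. The uniform could therefore move some sellers from asking to ejecting, and the asked-age difference would shrink although sellers had become stricter. A reader might then credit the uniform with a smaller effect on verification, and no planned table would show how many sellers ejected on sight.

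A second worry is the blank purchase item. If software dropped those visits as missing, the primary comparison would lose some of its clearest refusals.

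**Working it through.** The plan states no rate of asking or ejection, so there is no figure of its own to reproduce. All rates below are assumed.

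**1. How each response scores**

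| Seller's response | Q. 21 | Q. 22 | Purchase |
|---|---|---|---|
| Sells with no check | No | No | Yes |
| Ejects without asking | No | normally No | blank, no sale |
| Ejects after asking age | Yes | either | blank, no sale |
| Ejects over missing ID | either | normally Yes | blank, no sale |

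Only the second row raises the issue. The primary outcome separates it from the first.

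**2. Size of the effect on asked age**

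Let r be the share ejecting unasked and a the share of the remaining sellers who ask. Asked age = (1 − r)a.

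- Scenario 1, casual arm: r = 0.03, a = 0.40, giving 0.97 × 0.40 = 38.8%. Uniform arm: a = 0.50.
- Scenario 2, casual arm: r = 0.02, a = 0.50, giving 0.98 × 0.50 = 49.0%. Uniform arm: a = 0.80.

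| Uniform r | Scenario 1 difference | Scenario 2 difference |
|---|---|---|
| same as casual | +9.7 | +29.4 |
| 5% | +8.7 | +27.0 |
| 10% | +6.2 | +23.0 |
| 20% | +1.2 | +15.0 |

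The difference reaches zero at r = 1 − 0.388/0.50 = 22.4% in scenario 1 and r = 1 − 0.490/0.80 = 38.8% in scenario 2.

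For power, take 540 stores per arm (1,080/2) and the SAP 1.4 design effect 1 + (4 − 1) × 0.5 = 2.5, so 540/2.5 = 216 effective stores per arm. Suppose 35% in the uniform arm and 20% in the casual arm either ask or eject unasked. A test of that combined behaviour has 94% power. If 5% and 1% of stores are unasked ejections, asking alone is 30% against 19%, with 76% power. If they are 10% and 2%, it is 25% against 18%, with 42.5% power.

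**3. Diluted from what?**

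In scenario 1 with 10% ejection, the asked-age difference is 45.0 − 38.8 = 6.2 points. Three references are possible:

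- the same outcome with equal ejection: 9.7 points;
- asking among sellers who engage: 50 − 40 = 10.0 points;
- asking or ejecting: (10 + 45.0) − (3 + 38.8) = 13.2 points.

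These are different quantities. The plan estimates the randomised effect on asking, which under these inputs is 6.2 points, and estimates it correctly.

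**4. What the planned results show**

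Stay with that case and assume that 90% of engaged sellers who do not check go on to sell.

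- Unchecked sales: uniform 0.90 × 0.50 × 0.90 = 40.5%; casual 0.97 × 0.60 × 0.90 = 52.4%; difference −11.9 points.
- Stores with no check: uniform 100 − 45.0 = 55.0%; casual 100 − 38.8 = 61.2%.
- Sale rate among them (SAP 2.3.5): 40.5/55.0 = 73.6% against 52.4/61.2 = 85.6%.
- Unchecked and unsold: 55.0 − 40.5 = 14.5% against 61.2 − 52.4 = 8.8%.

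The last line is an upper bound on unasked ejections in each arm, obtained from planned outputs.

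**5. The blank purchase item**

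Let q be the share of checking sellers who still sell, in both arms. Primary rate = (1 − r)[(1 − a) × 0.9 + aq].

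| q | Ejection coded no sale | Blanks dropped |
|---|---|---|
| 0.2 | 49.5 − 60.1 = −10.6 | 55 − 62 = −7.0 |
| 0.3 | 54.0 − 64.0 = −10.0 | 60 − 66 = −6.0 |
| 0.5 | 63.0 − 71.8 = −8.8 | 70 − 74 = −4.0 |

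The right-hand column would matter, but nothing in the documents proposes that handling. The outcome is a completed purchase, and an ejected buyer made none. Protocol 8.7 does not extend its available-data rule to the outcomes.

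**The case for a change.** The strongest case for a change is that the tool records this behaviour and the analysis ignores it. The planned outputs also pool ejection on sight with refusal after a conversation. The 14.5% above could be 10% ejected plus 4.5% refused later, or 3% plus 11.5%. Asking among engaged sellers would be 45.0/90 = 50.0% in the first case and 45.0/97 = 46.4% in the second. That stands: the split is not a planned result.

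The supporting evidence is thinner than it looks. Protocol 8.7 ties being asked to leave to lack of proof of age, which points to visits where age or ID was raised and which Question 22 or the ID option would normally capture. The script passage "The seller might claim that the e-cigarette and cartridges are sold as a set" could suggest that many unchecked non-sales are commercial. It describes no failed purchase; it tells the buyer to insist on the cartridges alone. No passage gives an ejection rate or says that it differs by arm. The first option of Question 23 records no reason, and the buyers who complete it know the attire.

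A by-arm tabulation of Question 23 would be cheap and informative. It would have to be limited to stores where the buyer reached Questions 21 to 23, because a negative answer to Question 7 or 14 ends the form earlier. It would be added description and would alter no planned comparison. Question 26 is blanked by the same skip, so the report should state the denominator for dissuasion. That is a reporting detail and does not bear on the age-check outcomes.

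**Conclusion.** No change is needed. The scoring overlap is real, but asked age and requested ID are valid measures of what they name. A seller who ejects without asking has not verified age; that seller has refused a sale, which is the other limb of the hypothesis and the primary outcome. The tests would stay as they are, and the planned purchase rates already show the reaction to the uniform and cap the unasked ejections.

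The possible shrinkage depends wholly on assumed inputs. With equal ejection in scenario 1 the difference is 9.7 points against 10.0 among engaged sellers, which is negligible. At 10% ejection in the uniform arm against 3% in the casual arm it is 6.2 points. The difference vanishes only at 22.4% in scenario 1 and 38.8% in scenario 2. The missing coding sentence for Question 37 is a gap that an analyst fills correctly from the outcome definition: an ejection is a no-sale and the store stays in the denominator. Tabulating Question 23 by arm is an optional addition to the report.
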